6.1.2 Treatment arms/group

At baseline, all participants will be randomized 1:1 to one of the two treatment groups:

- **Inclisiran Group:** 100 participants. Treated with inclisiran sodium 300mg s.c. on Day 1, Day 90 and Day 270, and with matching placebo s.c. on Day 180.
- **Control Group:** 100 participants. Treated with matching placebo s.c. on Day 1 and Day 90, and with inclisiran sodium 300mg on Day 180 and Day 270.

Subcutaneous injections of the Inclisiran/placebo will not be dispensed to the participants but rather administered by qualified personnel at the study site on Day 1, Day 90, Day 180 and Day 270.

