9.2.3 Treatments

The SAF will be used for the analyses in this section.

Study treatment

The number and percentage of participants receiving study dose at each dosing visit will be summarized by treatment group. The number of doses received during the core part (excluding Day 180 dose) and during the extension part (including Day 180 dose) will also be summarized by treatment group.

Prior and concomitant therapies

Prior or concomitant medications will be summarized for the SAF in separate tabulations based on the coding dictionary used. Medications will be presented in alphabetical order, by Anatomical Therapeutic Chemical (ATC) class and preferred terms. Tables will show the overall number and percent of participants receiving at least one drug of a particular ATC class and at least one drug in a particular preferred term.

Prior medications and significant non-drug therapies will be summarized by treatment group. Concomitant medications and significant non-drug therapies prior to and after the start of the study treatment will be summarized by treatment group and by part.

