2. Participants randomized to Inclisiran Group will be treated with inclisiran sodium 300mg s.c. on Day 1 and Day 90 and Day 270, and with matching placebo s.c. on Day 180. Participants randomized to Control Group will be treated with matching placebo s.c. on Day 1 and Day 90, and with inclisiran sodium 300mg on Day 180 and Day 270.
3. The end of core part visit. The database lock for the core part is planned to occur after all randomized participants have completed the EOC visit (or have discontinued from the study before EOC). The primary endpoint analysis will be conducted after the database lock for the core part.
4. Participants who discontinue from study should be scheduled for an Early Exit visit if they agree. This Early Exit visit is suggested to be scheduled at least 30 days after last injection. If not possible, to set an Early Exit visit as soon as possible is also acceptable.

On Day 1 (Baseline), approximately 200 eligible participants who meet all inclusion and not meet any exclusion criteria will be randomized 1:1 to Inclisiran Group and Control Group. Study visits of core part will occur on Day 1 (baseline visit), Day 30, Day 90, Day 150, and Day 180. On Day 1 and Day 90 visits, inclisiran s.c. or placebo s.c. will be administered at the site by a healthcare professional. The primary endpoint will be assessed at Day 150. The EOC visit will be conducted on Day 180.

The extension part starts with a dose on Day 180 after all core part assessments are completed. In order to maintain the blind for the treatment group assignment, participants randomized to Control Group will receive inclisiran, while participants randomized to Inclisiran Group will receive placebo on Day 180. All participants will then receive inclisiran sodium 300 mg on Day 270, which will be the third dose of inclisiran for Inclisiran Group, and the second dose of inclisiran for Control Group. All injections will be administered at the site by a healthcare professional. The EOS visit (Day 360) will be the last visit of the study.

The randomization will not be stratified.

The core part analyses will be conducted when all randomized participants have completed the visit at Day 180 (or have discontinued from the study). The final analyses will be conducted when the trial ended. No interim analyses are planned.

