### Switching date

The switching date will be defined using the following algorithm.

- For participants with non-missing Day 180 study treatment dose date, the switching date will be set to the Day 180 study treatment dose date.
- For participants with missing Day 180 study treatment dose date and non-missing Day 180 visit date, the switching date will be set to the Day 180 visit date.
- For participants with missing Day 180 study treatment dose date and missing Day 180 visit date, the switching date will be set to the study day 195 date.

If the resulting switching date locates after the study discontinuation date or the analysis cutoff date (if any), the switching date will be set to missing and the participant will be considered to have not switched until the study discontinuation or the analysis cutoff.

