## Assessments and events allocation

In general, assessments and events will be allocated into the screening period, the core part and the extension part using the following rules.

- For non-randomized participants, all assessments / events will be considered as screening period assessments / events.
- For randomized participants, assessments / events with assessment date / event date prior to the randomization visit date will be considered as screening period assessments / events.
- For randomized participants with missing switching date, assessments / events with assessment date / event date on or after the randomization visit date will be considered as core part assessments / events.
- For randomized participants with non-missing switching date, assessments / events with assessment date / event date on or after the randomization visit date and on or prior to the switching date will be considered as core part assessments / events.
- For randomized participants with non-missing switching date, assessments / events with assessment date / event date after the switching date will be considered as extension part assessments / events.

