## Study treatment allocation

In general, study treatments will be allocated using the following algorithm.

- Study treatments at the randomization visit and Day 90 will be considered as core part study treatments.
- Study treatments at Day 180 and Day 270 will be considered as extension part study treatments.

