### **2.4.1 Study treatment / compliance**

The number and percentage of participants receiving study dose and the injection site location will be summarized by study visit and treatment group for both core part analyses and final analyses. For core part analyses, the summary tables including Day 1 and Day 90 visit and for overall study will be provided. For final analyses, the summary table will include Day 180, and Day 270 visit using OLS.

The number of doses received during the core part (at Day 1 and Day 90), duration of exposure, patient year of exposure will be summarized by treatment group for core part analyses. Such summary table of exposure to study treatment and listing for overall study will also be provided in core part analyses. The number of doses received during the whole study, duration of exposure for overall study and patient year of exposure will be summarized by treatment group for final analyses. Listings for overall study will also be provided in final analyses.

Duration of exposure for overall study will be calculated as: minimum of (Date of last dose of treatment – Date of first dose of treatment + 1 + 180, Date of last known visit – Date of first dose of treatment + 1). Duration of exposure to study treatment for overall study will be truncated at the analysis cutoff date for core part analyses.

The number of doses received during the extension part (at Day 180 and Day 270), duration of exposure in extension part and patient year of exposure will also be summarized by treatment group using OLS for final analyses. Duration of exposure for extension part will be calculated as: minimum of (Date of last dose of treatment in extension part – Date of treatment at Day 180 + 1 + 180, Date of last known visit in extension part – Date of treatment at Day 180 + 1). If the Day 180 treatment was not taken, then the date of Day 180 visit will be used.

Patient-year of exposure will be calculated as duration of exposure/365.25.

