### 2.7.1 Adverse events (AEs)

An AE will be counted as a treatment emergent AE (TEAE) if the AE started after the first dose of study treatment or the AE present prior to start of study treatment but increased in severity based on preferred term. Since the investigators are required to enter any worsened AE as a separate record, implementation-wise an AE is a TEAE as long as its start date is on or after date of first dose of study treatment. All TEAEs will be classified into core part TEAEs and extension part TEAEs.

- The core part TEAEs will be defined as TEAEs with the start date on or prior to the switching date.

- The extension TEAEs will be defined as TEAEs with the start date after the switching date.

Overall summary of TEAE will be displayed by treatment group and study part. The number (and percentage) of participants with TEAEs will be summarized:

- By study part, treatment group, primary system organ class (SOC) and preferred term (PT).
- By study part, treatment group, SOC, PT and maximum severity.
- By study part, treatment group, PT.
- By study part, treatment group, SOC and PT for TEAEs leading to study drug discontinuation.
- By study part, treatment group, SOC and PT for TEAEs related to study drug.

The number (and percentage) of participants with treatment emergent serious adverse events (TESAE) will be summarized:

- By study part, treatment group, SOC and PT.
- By study part, treatment group, SOC and PT for TESAEs related to study drug.

In core part analyses, the number (and percentage) of participants with TESAE will also be summarized for overall study:

- By treatment group, SOC and PT.
- By treatment group, SOC and PT for TESAEs related to study drug.

Unless otherwise specified, SOCs will be sorted alphabetically and, within each SOC, the PTs will be sorted in descending order of frequency. If a participant reported more than one adverse event with the same PT, the AE will be counted only once. A participant with multiple adverse events within a SOC is only counted once towards the total of the SOC. In case of summary by severity or relationship to study drug, summary will be done using the most severe or related occurrence respectively. Listing of all AEs and SAEs will be provided in both core part analyses and final analyses, regardless of whether they are treatment emergent.

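### Same-day reactions to the Day 180 injection are counted as core-part events, so reactions to the Control Group's first inclisiran dose appear under Control in the placebo-controlled safety tables

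*SAP*

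**What the plan says.** Three SAP rules set the boundary between the two parts for a participant dosed at Day 180.

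- Switching date (SAP 2.1.1): "For participants with non-missing Day 180 study treatment dose date, the switching date will be set to the Day 180 study treatment dose date".
- General allocation (SAP 2.1.1): after randomization, events dated "on or prior to the switching date will be considered as core part assessments / events".
- Adverse events (SAP 2.7.1): "The core part TEAEs will be defined as TEAEs with the start date on or prior to the switching date". Only events with a later start date go to the extension part.

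The injection itself is placed on the other side of the boundary.

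- SAP 2.1.1, study treatment allocation: "Study treatments at Day 180 and Day 270 will be considered as extension part study treatments".
- The core dose summary in SAP 2.4.1 covers only the first two visits: "The number of doses received during the core part (at Day 1 and Day 90"). Protocol 9.2.3 agrees, with separate counts for "The number of doses received during the core part (excluding Day 180 dose) and during the extension part (including Day 180 dose").
- What is injected that day (SAP 1.1): "participants randomized to Control Group will receive inclisiran, while participants randomized to Inclisiran Group will receive placebo on Day 180". The same section calls the Day 270 dose the Control Group's second inclisiran dose, so Day 180 is its first.

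SAP 2.7.1.1 names injection site reaction as an event of special interest. It tabulates these reactions by treatment group and study part, and measures time to onset from the latest administration of study drug.

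**The concern.** The dose is an extension treatment, but a reaction to it on the same date is a core event. The core Control column can then contain reactions to inclisiran, caused by an injection that the core dose count leaves out. The mirror image holds in the Inclisiran Group, where same-day reactions to the Day 180 placebo injection move into core.

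Two things make this matter. Protocol 2.3 identifies injection-site events as the only inclisiran-related adverse drug reaction, and safety compared with placebo during the core part is a stated secondary objective. If inclisiran causes more reactions than placebo, as the protocol says, the rule narrows the core contrast and understates a known harm. The extension tables also lose the earliest reactions to the Control Group's first inclisiran dose.

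**Working it through.** **The rule applied.** Take a participant dosed at Day 180, so that the switching date is the dose date.

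| Event start date | Part under SAP 2.7.1 | Part of the Day 180 dose |
|---|---|---|
| Day before the dose | Core | Extension |
| Same day as the dose | Core | Extension |
| Day after the dose | Extension | Extension |

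The mismatch is in the middle row. Protocol 1.3 requires assessments at dosing visits to precede the injection, so the inclusive boundary is right for laboratory values and vital signs. It is wrong for reactions that can only follow the injection. The SAP also treats its dosing days differently: under 2.7.1 an event dated on the first-dose date counts as treatment-emergent, that is, as following the dose, while an event dated on the Day 180 dose date is placed with the period before that dose.

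**Shift per participant.** Protocol 6.1.2 gives the Control Group as "100 participants. Treated with matching placebo s.c. on Day 1 and Day 90, and with inclisiran sodium 300mg on Day 180 and Day 270", and the Inclisiran Group is the same size. Each Control participant with a same-day Day 180 reaction and no earlier core reaction raises core Control incidence by 1/100 = 1.0 percentage point. The core difference falls by as much, offset by 1.0 point for each Inclisiran participant with a same-day reaction to the Day 180 placebo and no earlier core reaction.

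**Onset categories.** An extension-part onset falls on a later date than the Day 180 dose, so it is at least 24 − T hours after an injection given at hour T: 16 h for T = 8, 14 h for T = 10, and more than 12 h for any T below 12. For a morning injection, no reaction to that injection can enter the extension categories of up to 4 h or of 4 to 12 h. Day 270 reactions still can.

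**Illustration of size.** The documents give no plan figure to reproduce. Let p and q be the reaction risks per inclisiran and per placebo injection, and f the share of reactions starting on the injection date. Everyone is dosed at Day 180. The values p = 0.05 and q = 0.005 are assumed.

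If injections are independent:

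- Correct core difference = [1 − (1−p)²] − [1 − (1−q)²] = 0.0975 − 0.009975 = 8.75 points.
- As written = [1 − (1−p)²(1−qf)] − [1 − (1−q)²(1−pf)].
- Points lost = f(p−q)(1−pq) = f × 0.045 × 0.99975 = 4.50f.

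If the same people react every time, with placebo reactors a subset of inclisiran reactors:

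- Correct difference = p − q = 4.50 points.
- As written = (p−q)(1−f), so points lost = 4.50f.

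| f | Independent: 8.75 becomes | Shrinkage | Dependent: 4.50 becomes | Shrinkage |
|---|---|---|---|---|
| 10% | 8.30 | 5.1% | 4.05 | 10% |
| 50% | 6.50 | 25.7% | 2.25 | 50% |
| 95% | 4.48 | 48.8% | 0.23 | 95% |

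The relative loss is close to f/2 under independence and equals f under full dependence. It hardly depends on p: with p = 0.02 or 0.08 the independent shrinkage is 25.3% to 26.1% at f = 50%. The points lost are positive whenever p exceeds q, which fixes the direction under both models.

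**The case against.** The strongest reply is that this is a narrow date convention of unknown size. The illustration assumes both rates, the same-day share and the dependence between injections, and its shrinkage mostly returns the assumed share. The extreme case needs nearly all reactions to start the same day in the same people. That is correct: only the 1.0 point per participant rests on the documents.

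Several points limit the consequence, and they stand. Safety is descriptive and efficacy is untouched. Protocol 2.3 describes these reactions as localized, transient and mostly mild. SAP 2.7.1.1 provides an injection-site listing in both analyses and repeats the summaries for the overall study in the final analyses, so the cases can be traced. SAP 2.4.1 also puts an overall-study exposure summary into the core analyses, so Day 180 doses given by the cutoff are reported there.

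These points do not remove the mismatch. The overall-study tables mix placebo and inclisiran injections within each group, so they cannot replace the core comparison, and the core-only dose count still omits the Day 180 injection. Analysing the safety set by treatment actually received does not help either: it classifies participants and has no rule by dose or part. Protocol 9.4.2 allocates events by start date but sets no same-day rule.

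It is also fair that adverse events are generally recorded by date (Protocol 8.6.1). Moving every same-day event to the extension would misplace those that began before the injection. Programming specifications and table shells are not among the documents, so the absence of an exception is established only for the visible text.

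**Conclusion.** The concern holds. Followed exactly, the SAP counts same-day reactions to the Control Group's first inclisiran injection in the Control column of the core safety tables and omits them from the extension tables. The expected direction is to understate the core inclisiran-placebo difference in injection site reactions, given the protocol's own statement that inclisiran causes more of them.

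Confidence is high in the reading of the rule and low in the size of the effect. Under the assumed inputs, the shrinkage runs from about 5% to 95% over same-day shares of 10% to 95% and the two dependence models. That range shows what the rule can do and is not an estimate for this trial. This should be fixed, but it does not threaten the primary conclusion.

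**What to change.** In SAP 2.1.1 (event allocation) and 2.7.1, when a Day 180 dose was given, allocate to the extension part:

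- any injection site reaction starting on that date whose most recent administration is the Day 180 injection, which reuses the timing rule already in SAP 2.7.1.1;
- any other adverse event with a documented onset time after that injection.

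Keep the present inclusive boundary for all other same-day adverse events, for all assessments, and for participants without a Day 180 dose. Do not allocate by judged causality.

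The cost is SAP wording and one programming rule if the core tables have not been produced. They may have been: Amendment 2 is marked only as preceding the final database lock, and SAP 2.1 foresees repeating core analyses only after major changes in core data. In that case, give the corrected tables in the final CSR, labelled as a post-lock change. Some other same-day events without an onset time will stay in core.

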- The overall study duration is approximately 374 days but can vary depending on individual screening and the visit window.
- Participants will receive inclisiran/placebo subcutaneous injections on Day 1, Day 90, Day 180. And all participants will receive inclisiran treatment on Day 270.
- Visits will be on Day 1, Day 30, Day 90, Day 150 (primary endpoint), Day 180 (end of core part, EOC), Day 210, Day 270, Day 330 and Day 360 (EOS).

Treatment of interest

For primary estimand, the treatment of interest is inclisiran sodium 300 mg s.c. at Day 1 and Day 90 as monotherapy (no other lipid lowering therapy) comparing to matching placebo s.c. at Day 1 and Day 90 as monotherapy, regardless of study treatment discontinuation.

Number of Participants:

Approximately 200 participants will be randomized 1:1 to inclisiran and placebo .

Key Inclusion criteria

- Written informed consent must be obtained before any assessment is performed
- Adults ≥ 18 and ≤ 75 years of age
- Fasting LDL-C value of ≥ 130 mg/dL but <190 mg/dL at screening
- Triglycerides ≤ 400 mg/dL at screening

- Categorized as low or moderate ASCVD risk by the 2016 Chinese guideline for the management of dyslipidemia in adults at screening
- No plan of introducing other lipid lowering therapy during the study participation

Key Exclusion criteria

- Use of any lipid-lowering therapy within 90 days prior to screening visit
- Previous exposure to inclisiran or any non-mAb PCSK9-targeted therapy, either as an investigational or marketed drug within 2 years prior to screening visit
- History of ASCVD
- Diabetes mellitus or fasting plasma glucose at screening \geq 7.0 mmol/L or glycated hemoglobin (hemoglobin A1c) (HbA1c) \geq 6.5%
- Active liver disease defined as any known current infectious, neoplastic, or metabolic pathology of the liver or unexplained elevations in alanine aminotransferase (ALT), aspartate aminotransferase (AST), >3 x the upper limit of normal (ULN), or total bilirubin >2 x ULN at screening
- Estimated glomerular filtration rate (eGFR) $<$ 30 mL/min/1.73m² at screening

Treatment Groups:

At Day 1 (Baseline), all participants will be randomized 1:1 to one of the two treatment groups:

- **Inclisiran Group:** 100 participants. Treated with inclisiran sodium 300mg s.c. on Day 1, Day 90 and Day 270, and with matching placebo s.c. on Day 180.

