- **Control Group:** 100 participants. Treated with matching placebo s.c. on Day 1 and Day 90, and with inclisiran sodium 300mg s.c. on Day 180 and Day 270.

[figure not shown]
Steering Committee: Yes (see Section 10.1.4 Committees Structure)

Key words

Inclisiran, LDL-C, monotherapy

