## 2.2 Analysis sets

The following analysis sets will be used for statistical analyses:

The **Screened Set (SCR)** consists of all participants who signed the informed consent. The SCR includes only unique screened participants, i.e., in the case of re-screened participants only the chronologically last screening data is counted.

The **Randomized Analysis Set (RAS)** consists of all participants who received a randomization number, regardless of receiving trial medication.

The **Full Analysis Set (FAS)** consists of all randomized participants with the exception of those participants who have not been qualified for randomization and have not received study drug but have been inadvertently randomized into the study. Following the intent-to-treat (ITT) principle, participants will be analyzed according to the treatment they have been assigned to at randomization. Efficacy variables will be analyzed based on the FAS.

The **Safety Analysis Set (SAF)** includes all participants who received at least one dose of study drug. Participants will be analyzed according to the study treatment actually received. The SAF will be used for the analyses of safety variables.

[figure not shown]
The **Open-label Set (OLS)** includes all participants who entered the extension part and received at least one dose of study drug during extension part (at Day 180 or Day 270). OLS will be used to analyze the non-efficacy data in extension part, unless otherwise specified.

Participants without valid written informed consent will be excluded from all analysis sets. Further exclusions from the FAS are only justified in exceptional circumstances (e.g., site closed down for GCP reasons). The determination of which participants were excluded from the FAS is made in a blinded manner before the database lock for the Core Part.

Rules leading to exclusion from the analysis sets are given in [Appendix 5.5](#).

Note: The last part of the definition of the FAS is what is often referred to as mis-randomized participants i.e. participants for whom IRT calls were made by the site either prematurely or inappropriately prior to confirmation of the participant's final randomization eligibility and study medication was not administered to the participant. These participants would subsequently not continue to take part in the study or be followed-up. Mis-randomized participants will not be included in the FAS, but they will be included in the RAS.

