## 2.7 Safety analyses

For all safety analyses, the SAF will be used, unless otherwise specified. All listings and tables will be presented by treatment group. Baseline data will be summarized where appropriate (for change from baseline summaries).

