The number of deaths resulting from SAEs suspected to be related to study treatment and SAEs irrespective of study treatment relationship will be provided by study part, treatment group, SOC and PT.

For above by-part summary tables, OLS will be used for extension part data in final analyses. Besides, above summary tables for overall study will also be provided using SAF in final analyses. Subgroup analyses for safety will be performed in subgroups as specified in [Section 2.2.1](#). Overall summary of TEAE by subgroup will be provided by treatment group in core part analyses. Subgroup analyses of all treatment emergent adverse events (TEAE) will also be displayed by treatment group, SOC and PT in core part analyses. The number (and percentage) of participants with TEAEs will be provided for each category of subgroup.

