### **AE reporting for CT.gov**

For the legal requirements of clinicaltrials.gov, two required tables on treatment emergent adverse events which are not serious adverse events with an incidence greater than X% (X will

be selected prior to final database lock)\* and on treatment emergent serious adverse events and SAE suspected to be related to study treatment will be provided by SOC and PT on the safety set population.

If for a same patient, several consecutive AEs (irrespective of study treatment causality, seriousness, and severity) occurred with the same SOC and PT:

- a single occurrence will be counted if there is  $\leq$  1 day gap between the end date of the preceding AE and the start date of the consecutive AE
- more than one occurrence will be counted if there is  $>$  1 day gap between the end date of the preceding AE and the start date of the consecutive AE

For occurrence, the presence of at least one SAE / SAE suspected to be related to study treatment / non SAE has to be checked in a block e.g., among AE's in a  $\leq$  1 day gap block, if at least one SAE is occurring, then one occurrence is calculated for that SAE.

The number of deaths resulting from SAEs suspected to be related to study treatment and SAEs irrespective of study treatment relationship will be provided by SOC and PT.

These summaries will be provided only after full study completion.

\*Note: the X% has been chosen as 5% before the final database lock.

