## **3 Sample size calculation**

This study is designed to randomize approximately 200 Participants (with randomization ratio of 1:1 to inclisiran and placebo arms) in order to provide adequate information to characterize the safety profile of inclisiran as well as to have sufficient power for the primary efficacy endpoint.

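### Overall-study safety tables, and probably the registry tables, mix placebo-period and inclisiran-period events under one Control label, and no visible table pools all inclisiran-exposed participants

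*SAP*

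**What the plan says.** **Dosing.** Protocol 1.1 describes the Control Group as "Treated with matching placebo s.c. on Day 1 and Day 90, and with inclisiran sodium 300mg s.c. on Day 180 and Day 270" and the Inclisiran Group as "Treated with inclisiran sodium 300mg s.c. on Day 1, Day 90 and Day 270, and with matching placebo s.c. on Day 180".

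**Columns and counting.** SAP 2.7 says of the safety output: "All listings and tables will be presented by treatment group". Under SAP 2.7.1 an adverse event is treatment-emergent if it starts on or after the first dose of study treatment, whether that dose is placebo or inclisiran. SAP 2.2 defines the safety set (SAF) with the rule "Participants will be analyzed according to the study treatment actually received". It does not say how to show a participant who has received both.

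**Tables.** Most AE tables are given by study part, and "OLS will be used for extension part data in final analyses". The OLS requires a dose at Day 180 or Day 270. In addition, the "above summary tables for overall study will also be provided using SAF in final analyses". SAP 2.7.1.1 (events of special interest, injection-site reactions) and 2.7.2 (deaths) also plan overall-study tables. The registry tables "will be provided by SOC and PT on the safety set population", after full study completion, with no stated split by part or by current treatment.

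**Core/extension boundary.** The switching date in SAP 2.1.1 is the Day 180 dose date. If there was no such dose it is the Day 180 visit date, or failing that study day 195. Events starting on the switching date count as core. The Day 180 dose itself is allocated to the extension.

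**Purpose.** SAP 3 gives "adequate information to characterize the safety profile of inclisiran" as one reason for randomising about 200 participants.

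**The concern.** In an overall-study table the Control column is neither a placebo column nor an inclisiran column. Anyone who reads it as the comparator will see a smaller relative effect than the randomised period showed. This matters most if the registry tables take the same form, because they are the public record.

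The extension by-part tables do show Control participants on inclisiran. However, no visible table counts every participant from the first inclisiran dose, which is the natural display for a trial sized partly to describe inclisiran safety.

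The by-part tables also have two gaps:

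- A participant who had inclisiran in the core part, gets no extension dose and stays in follow-up can have events after the switching date. Those are extension events, but the participant is not in the OLS. They appear only in the overall-study tables and the listings.
- A Control participant who reacts to the first inclisiran injection on the day it is given has an event dated on the switching date. It is tabulated as a core-part Control event, that is, as if on placebo. Injection-site events are the only adverse drug reaction that Protocol 2.3 identifies, and SAP 2.7.1.1 uses onset bands starting at 4 hours or less.

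**Working it through.** **Inputs from the documents.** 100 participants per group; 180 core days and 180 extension days (Protocol 6.1.3: 14 + 180 + 180 = 374 days, which reproduces). Inclisiran Group: 3 inclisiran and 1 placebo injections. Control Group: 2 of each. Neither document gives a safety precision figure for the sample size of 200, so there is none to reproduce. Event rates are not given either; those below are assumptions, shown over a range. Full attendance is assumed.

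**Inclisiran exposure**

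- Inclisiran Group: 100 × 360 / 365.25 = 98.6 person-years; 300 doses.
- Control from Day 180: 100 × 180 / 365.25 = 49.3 person-years; 200 doses.
- Together: 147.8 person-years and 500 doses in up to 200 participants. Control supplies 49.3/147.8 = 33% of the time, 200/500 = 40% of the doses and 100/200 = 50% of the people.
- Under the Control label, 180 of 360 days (50%) are placebo time.

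**Bound on the overall ratio.** Let the event rate be λ on placebo and rλ on inclisiran, constant in time. The Inclisiran column averages rλ and the Control column (λ + rλ)/2, so the overall ratio is 2r/(1 + r). For r = 2, 3 and 5 this is 1.33, 1.50 and 1.67. It can never exceed 2.

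**Risks.** For time-related events with 6-month risks p1 (inclisiran) and p0 (placebo), the overall risks are 1 − (1 − p1)² and 1 − (1 − p0)(1 − p1). For events tied to injections, with per-injection risks p1 and p0, the core risks are 1 − (1 − p1)² and 1 − (1 − p0)². The overall risks are then 1 − (1 − p1)³(1 − p0) and 1 − (1 − p0)²(1 − p1)².

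| Assumed risk, inclisiran vs placebo | Core, % | Ratio; difference (points) | Overall, % | Ratio; difference (points) |
|---|---|---|---|---|
| 6-month, 5% vs 1% | 5.0 vs 1.0 | 5.0; 4.0 | 9.75 vs 5.95 | 1.64; 3.8 |
| 6-month, 8% vs 2% | 8.0 vs 2.0 | 4.0; 6.0 | 15.36 vs 9.84 | 1.56; 5.5 |
| 6-month, 10% vs 5% | 10.0 vs 5.0 | 2.0; 5.0 | 19.0 vs 14.5 | 1.31; 4.5 |
| Per injection, 2% vs 1% | 3.96 vs 1.99 | 1.99; 2.0 | 6.82 vs 5.87 | 1.16; 1.0 |
| Per injection, 2.5% vs 0.5% | 4.94 vs 1.00 | 4.95; 3.9 | 7.78 vs 5.89 | 1.32; 1.9 |
| Per injection, 5% vs 1% | 9.75 vs 1.99 | 4.90; 7.8 | 15.12 vs 11.55 | 1.31; 3.6 |

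The ratio shrinks in every row. The difference barely moves for time-related events and roughly halves for injection-related ones.

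**Same-day Day 180 reactions in the core table.** Take 2.5% and 0.5% per injection, and let a fraction f of Day 180 reactions start that day. The core risks become 1 − 0.975²(1 − 0.005f) for Inclisiran and 1 − 0.995²(1 − 0.025f) for Control.

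- f = 0: 4.9% vs 1.0%, ratio 4.95.
- f = 0.5: 5.2% vs 2.2%, ratio 2.3.
- f = 1: 5.4% vs 3.5%, ratio 1.6.

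**What pooling adds.** With no events seen, the one-sided 95% upper limit 1 − 0.05^(1/n) is 2.95% for n = 100 and 1.49% for n = 200. The chance of seeing at least one event of 1% risk, 1 − 0.99^n, is 63.4% and 86.6%. Both treat every participant as having the same risk, although Control has fewer inclisiran doses and less time.

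**The case against.** The stated safety objectives are inclisiran against placebo in the core part, and inclisiran in the extension part. The by-part tables answer both, and the overall-study tables are additions. Inclisiran Group and Control Group are defined in the protocol as whole dosing sequences, so an overall table by group can be read as describing sequences. This stands: the main safety comparison does not rest on the mixed column.

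Several stronger readings are tempting but not supported.

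- *Control's inclisiran exposure goes unused.* It is reported in the extension tables on the OLS. It is not pooled, and it is a third of inclisiran person-time and 40% of doses; half is right only as a head count.
- *The SAP contradicts its rule on treatment received.* The rule is silent on switched participants, which is a gap and not a contradiction.
- *The registry tables certainly pool the periods.* This is inferred from the safety set, the treatment-emergent definition and the timing. The column layout may be fixed in table shells that are not available here.
- *The mixed Control rate is mostly inclisiran events.* That depends on the event. Where rates are similar on both treatments, about half would come from placebo time.

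A reader could nearly rebuild a pooled count by adding the overall Inclisiran column to the extension Control column, since the two do not overlap. The sum would miss same-day reactions to Control's first inclisiran dose. The total column mentioned for events of special interest does not serve: overall it includes placebo time, and in the extension it omits core events. Parts of the SAP are redacted, so a pooled table there cannot be excluded.

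**Conclusion.** The point holds as a weakness in supplementary safety reporting with an inexpensive remedy. The overall-study AE, special-interest and death tables mix placebo and inclisiran periods under Control, and the registry tables probably do too. Under constant rates the overall ratio cannot exceed 2 whatever the true ratio. Under the assumed rates a core ratio near 5 appears as 1.6 for time-related events, with almost the same absolute difference, and as 1.3 for injection-related events. Those sizes rest on assumed rates; the direction does not, provided the event is more frequent on inclisiran.

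A reader might conclude that the trial's safety comparison as a whole is diluted. The documents do not support that, because the core-part tables keep the randomised contrast. The exception is the Day 180 boundary rule, which can place same-day reactions to inclisiran in the core Control column. Its effect depends on the share of reactions with same-day onset, which the documents do not give.

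Pooling would raise the described inclisiran exposure from about 99 to about 148 person-years and from 100 to up to 200 participants, assuming full attendance.

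**What to change.** 1. In the overall-study and registry tables, assign each event to the treatment in effect at onset. Split Control into a placebo period and an inclisiran period that begins at the first inclisiran dose, scheduled for Day 180. State the registry column layout in the SAP.
2. Count events that start after the Day 180 injection as extension events, in line with the allocation of that dose to the extension. SAP 2.7.1.1 already needs onset in hours for injection-site reactions. For events recorded by date only, state a convention; SAP 2.7.1 already treats events on the date of the first dose as post-dose.
3. Add an any-inclisiran column that counts all participants from their first inclisiran dose, whether or not they are in the OLS, with exposure-adjusted rates. This also captures later events in participants with no extension dose.

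The data are already to be collected. The cost is extra derivation and programming across the AE, SAE, death, special-interest and injection-site tables. The pooled column is not a randomised comparison and must be labelled so, and its participants differ in number of doses and length of exposure.
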